#### **3.1 Statistical hypothesis for trial objectives**

**The primary endpoint is time to colorectal cancer screening by end of follow up at 12 months.** This will be determined by a review of subjects' electronic medical records and patient self-report. Subjects for whom a screening result is not recorded in the

EMRs will be classified based on patient self-report of screening. The hypothesis to be tested is that an intervention which provides subjects with their colorectal cancer risk information, compared to not providing this information, increases colorectal cancer screening rates based on the primary endpoint.

### **3.2 Sample Size justification**

A clinically significant improvement in the screening rate would be greater than or equal to 10-20%.

To calculate the appropriate sample size necessary for this study, we assumed uniform accrual over a 6-month period and minimum follow-up of 12 months for all subjects.

Further assuming that the current standard has a screening rate of 50% by 6 months (or event rate of 50%) and that the intervention will increase this rate to 65% (or event rate of 35%, leading to a hazard ratio of 1.5), a total of 225 subjects will be needed.

### **3.3 Randomization and blinding**

Subjects will be randomized 1:1 using block randomization stratified by gender (male/female) and age group (under 60 years old or 60 years old and over) to either the CRCRAT arm or control arm. The randomization scheme will be generated using the 'blockrand' package in R. The 'blockrand' function randomizes subjects to specified groups within sequential blocks; block sizes were randomly chosen from the set of 2, 4, 6, 8. The randomization scheme will be incorporated into REDCap in order to assign participants into the treatment groups. This is an open-label study with no blinding.

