Eligible subjects will be contacted using an approved telephone script to provide verbal consent for participation in the study. If a subject agrees to participate in the study, they will be immediately randomized, using blocked randomization, to either the CRCRAT or control arm. Both groups will then undergo a pre-intervention survey designed to assess attitudes towards colorectal cancer screening. Study interventions will be administered during this same telephone encounter. The control and intervention arms will both be read general information about colorectal cancer. The CRCRAT arm will then be guided through a series of questions from the NCI Colorectal Cancer Risk Assessment Tool in order to calculate their personalized risk of colorectal cancer. This personalized risk score will be recorded and subjects will be provided with the information on their risk scores. Immediately following these interventions, both arms will undergo a post-intervention survey, which again assesses attitudes towards colorectal cancer screening. Over the next 6 and 12 months, subjects' electronic medical records will be reviewed for colorectal cancer screening status. Subjects who were not screened, per their electronic medical record, will be contacted via phone or mail to see if they were screened elsewhere and/or assess their current screening intent. Subjects will be contacted no more than 3 total times for this research study.

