### **8.2. Primary Efficacy Endpoint**

#### **8.2.1. Definition**

The primary endpoint is time to colorectal cancer screening by end of follow up at 12 months. This will be determined by a review of subjects' electronic medical records. Subjects for whom a screening result is not recorded in the EMRs will be deemed to have not had colorectal cancer screening.

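### Outcome collection has no masking safeguard, although follow-up self-report can create screening events; whether this reaches the primary endpoint depends on reconciling sections 3.1, 8.2.1 and 8.2.2

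*Combined protocol and SAP*

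**What the plan says.** **Masking.** Section 3.3: "This is an open-label study with no blinding". No section describes masked record review, masked follow-up contact or masked adjudication.

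**Where the arm is visible.** Section 3.3: "The randomization scheme will be incorporated into REDCap in order to assign participants into the treatment groups". Section 3, on the enrolment call: "Study interventions will be administered during this same telephone encounter". For the CRCRAT arm only, section 3 adds: "This personalized risk score will be recorded and subjects will be provided with the information on their risk scores".

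**How the outcome is collected.** Section 3 says that over 6 and 12 months subjects' "electronic medical records will be reviewed for colorectal cancer screening status", and that those without a recorded screen "will be contacted via phone or mail to see if they were screened elsewhere". Total contacts are capped at three per subject in both arms.

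**What counts as an event.**
- Section 3.1 bases the primary endpoint on "electronic medical records and patient self-report".
- Section 8.2.1 uses the record alone: "Subjects for whom a screening result is not recorded in the EMRs will be deemed to have not had colorectal cancer screening".
- Section 8.2.2 accepts a self-reported screen that is absent from the record and dates it at the follow-up call.
- Section 8.3.1, items 1 and 2, uses self-report for the 12- and 6-month screening rates when the record is silent.

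The plan does not say who reviews records or makes follow-up contacts, what they can see in REDCap, whether the follow-up question is scripted, or whether a self-report is verified. The only script mentioned is the one for the consent call.

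**The concern.** Subjects who hear their own risk score cannot be masked. Staff who collect the outcome are a different matter, and the plan does not treat them separately.

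Several steps between a subject's screening and its entry in the dataset involve effort or judgement: how far to search a record for outside tests, how persistently to pursue a contact within the cap, how to put the question, and how to code an unclear answer. If staff know the arm, any of these can differ by arm without intent. Where self-report counts, such a difference adds events to one arm. Under section 8.2.2 the call date is also the event date, so the timing of calls enters the Cox model as well.

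At stake is whether a difference between arms reflects screening done or screening found. The trial's stated purpose is to decide whether to propose the tool for use in primary care clinics.

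**Working it through.** **1. Which endpoints are exposed**

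| Section | Endpoint | Self-report counts? | Can follow-up contact create an event? |
|---|---|---|---|
| 3.1 | Primary | Yes | Yes |
| 8.2.1 | Primary | No | No |
| 8.2.2 | Primary (analysis) | Yes, dated at the call | Yes |
| 8.3.1, item 1 | Screened at 12 months | Yes | Yes |
| 8.3.1, item 2 | Screened at 6 months | Yes | Yes |

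The secondary screening rates are exposed on any reading. The primary endpoint is exposed to follow-up contact under 3.1 and 8.2.2 but not under 8.2.1. Record review is without a masking provision throughout.

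**2. The plan's own figure**

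The illustration needs the number per arm, so the total of 225 in section 3.2 was checked first. Inputs from the plan are 50% against 65% screened by 6 months, two-sided 0.05 and 1:1 allocation. Power is not stated, so 80% is assumed, with exponential times.

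- Hazard ratio = ln 0.35 / ln 0.50 = 1.515.
- Events (Schoenfeld) = 4 × (1.960 + 0.842)² / (ln 1.515)² = 182.2, rounded up to 183.
- Probability of an event by 12 months: control 1 − 0.50² = 0.75; intervention 1 − 0.35² = 0.8775; mean 0.814.
- N = 183 / 0.814 = 225.

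The figure reproduces with 12 months of follow-up for everyone, giving 112.5 per arm. Masking changes none of this.

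**3. Illustration for the 12-month binary comparison (secondary endpoint)**

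Suppose no true effect and d extra ascertained screening in one arm. Then

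SE = √(2p(1 − p)/112.5), and type I error = P(|Z + d/SE| > 1.96).

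Both d and the range of p are assumptions; 0.75 is the plan's 50% at 6 months carried to 12 months under exponential times.

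| d | p = 0.30 (SE 0.0611) | p = 0.50 (SE 0.0667) | p = 0.75 (SE 0.0577) |
|---|---|---|---|
| 2 points | 0.062 | 0.060 | 0.064 |
| 3 points | 0.078 | 0.073 | 0.081 |
| 5 points | 0.130 | 0.117 | 0.139 |

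Example: p = 0.50 and d = 0.05 give d/SE = 0.75, and P(Z > 1.21) + P(Z < −2.71) = 0.113 + 0.003, or about 0.117. Five points is 0.05 × 112.5 = 5.6 subjects in one arm.

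**4. The same assumption carried to the Cox model**

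This applies only if self-report counts for the primary endpoint. With p = 0.75 and d = 0.05, the apparent hazard ratio is ln 0.20 / ln 0.25 = 1.16 and the events are 112.5 × (0.75 + 0.80) = 174. The shift is √(174/4) × ln 1.16 = 0.98, for a type I error of about 0.17; at 2 points it is about 0.07. This is rough: it assumes proportional hazards, whereas self-reported events would cluster at call dates.

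**The case against.** The strongest reply has four parts.

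**The primary endpoint may be record-only.** Under section 8.2.1 follow-up contact cannot create a primary event, and a dated in-system test leaves little room for judgement. This stands as a limit on the point. It does not dispose of it: sections 3.1 and 8.2.2 say the opposite, and the two screening-rate secondary endpoints use self-report in any case.

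**The rules are the same in both arms.** Records are reviewed at the same times, contact is triggered by the absence of a recorded screen, and the cap of three is common. Some contact may be by mail, where no caller elicits the answer. This limits differential pursuit, but a cap does not equalise effort, timing or wording beneath it.

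**Staff are not shown to know the arm.** A reader might infer from section 3.3 that reviewers and callers know each subject's allocation. The documents do not say so; they do not identify these staff or describe their REDCap access. What they support is that nothing prevents such knowledge.

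**Masking is not a matter of one setting.** A reader might infer that hiding the REDCap allocation field would suffice. It would not: the risk score is recorded in one arm only, whoever delivered the intervention already knows the arm, and subjects can disclose it. Nor does masking staff address unmasked subjects who report differently by arm. This stands, and it is why the remedy needs several parts.

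**Conclusion.** The point holds as a gap in the plan. The plan declares no blinding for any role and gives no safeguard for outcome collection, although self-report obtained at follow-up creates secondary events and, under sections 3.1 and 8.2.2, primary events. The exposure is concentrated in outside tests and self-report. For the primary endpoint it cannot be judged until 3.1, 8.2.1 and 8.2.2 agree.

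The size cannot be estimated from the documents. The range of about 6-14% rests on assumed differences of 2 to 5 points, 112.5 per arm, rates of 30-75% and no true effect, and it concerns a secondary endpoint. A reader might take it as the type I error of the primary analysis, or as evidence that bias is likely. It is neither: it shows what a difference of that size would do if it occurred. The change is worth making because the risk can be reduced cheaply.

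**What to change.** 1. **Reconcile sections 3.1, 8.2.1 and 8.2.2** on whether self-report counts for the primary endpoint.
2. **In sections 3 and 3.3**, state that subjects are unmasked, but that the 6- and 12-month record abstraction and contact lists are produced without the allocation field or any other arm-revealing item, including the CRCRAT risk score and post-intervention data. REDCap user rights can enforce this.
3. **Lock the record-based classification** before any follow-up contact.
4. **Use one fixed script** in both arms for the question about screening elsewhere.
5. **Where existing staffing allows**, have follow-up done by someone who did not deliver that subject's intervention.
6. **Add a record-only sensitivity analysis** for every endpoint that accepts self-report, because masking staff does not remove reporting bias from unmasked subjects.

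The cost is a few sentences in the plan, a REDCap permission set, a short script and one extra analysis. The sample size of 225 and the primary model stay as they are. The downside is imperfect masking: staff may remember subjects from the enrolment call, and subjects may reveal their arm.

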## **4. GENERAL ANALYSIS DEFINITIONS**

The general conventions to be used for the statistical analyses and presentation of the data are presented below. Departures from these general conventions may be given in the specific detailed sections of this analysis plan.

1. SAS Version 9 or R Version 3 will be the statistical software package used for all data analyses.
2. Continuous variables will be presented with mean, standard deviation, median (25th percentile, 75th percentile), minimum and maximum values. Categorical variables will be presented as number of subjects and percentage of number of subjects by levels of the variable.
3. The number and percentage of responses will be presented in the form XX (XX) where the percentage is in the parentheses. Unless otherwise specified, the denominator for percentages will be the number of subjects in a given intervention group within the analysis population of interest. The denominator will be included when it differs from the standard analysis population.
4. All summary tables will include the analysis population sample size (i.e., number of subjects).

5. Change from baseline (as applicable) will be calculated for each period as follows:  
Change from baseline = Post-baseline value – baseline value.
6. Date variables will be formatted as DD-MON-YYYY for presentation. In the case of missing day, month, and/or year information, “NA” will be presented. For example, a date with a missing month and day will be presented as NANAYYYY.
7. Unless otherwise stated, statistical comparisons will be performed using two-sided significance tests. An alpha level of 0.05 will determine significance unless otherwise noted for a specified analysis.
8. When count data are presented, the percentage will be suppressed when the count is zero in order to draw attention to the non-zero counts.
9. Unless specified otherwise, data will be presented by intervention and control subjects.

## **5. ANALYSIS SETS**

The Intent-to-treat (ITT) Analysis Set is defined as all randomized subjects. Subjects will be analyzed as per their randomized intervention assignments.

The Per-Protocol (PP) Analysis Set is defined as all randomized subjects for whom 12 month follow-up visit data are available.

## **6. INTERIM ANALYSIS AND DATA MONITORING COMMITTEE REVIEW**

We will not conduct any interim analysis. There is no data monitoring committee. Adverse events are not being reported or analyzed for this study.

## **7. SUBJECT INFORMATION**

### **7.1. Demographics and Baseline Characteristics**

We will summarize descriptive statistics (mean, median, standard deviation, minimum and maximum) by study arm for all endpoints. Categorical variables, such as gender, site, race, ethnicity and medical history will be summarized using frequencies and percentages. Graphical tools such as histograms and box plots and the 95% CI will also be presented if relevant. Transformations, including the log-transformation, will be considered when appropriate. In some cases, methods that rely on assumptions other than normality may be considered including non-parametric approaches such as the Wilcoxon rank sum test. For the secondary outcome of change in screening intent, a comparison of means accounting for repeated measures will be applied.

### **7.2. Disposition Information**

The disposition of all subjects who were randomized will be summarized including proportion completing the study, lost to follow-up, early termination and reasons for discontinuation (when available).

### **7.3. Protocol Deviations**

Protocol deviations will be summarized by randomization group. The categories of major protocol deviations may include, but are not limited to, the following:

- Subjects were randomized, but did not meet inclusion or exclusion criteria.

## **8. EFFICACY ANALYSIS**

Our primary efficacy analysis will be performed on the intent-to-treat population. We will also conduct efficacy analysis on the per-protocol population.

### **8.1. Analysis Specifications**

#### **8.1.1. Level of Significance**

Unless otherwise specified, all statistical tests will be interpreted at a 2-sided significance level of 0.05, and all confidence intervals at a 2-sided level of 95%.

#### **8.1.2. Data Handling Rules**

We anticipate minimal missing data in this study since we are obtaining information via telephone and medical record review and will contact subjects up to three times. We will include partial data for those subjects who do not complete the 12-month follow-up. We will fully describe missing data for each variable and any pertinent patterns of missingness (e.g. how missingness is related to specific baseline measurements or time, if at all). If missingness is an issue, we will rely on statistical methods including multiple imputation or mixed effects regression techniques that will allow for systematic missingness that is related to observed features.

### **8.2. Primary Efficacy Endpoint**

#### **8.2.1. Definition**

The primary endpoint is time to colorectal cancer screening by end of follow up at 12 months. This will be determined by a review of subjects' electronic medical records. Subjects for whom a screening result is not recorded in the EMRs will be deemed to have not had colorectal cancer screening.

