#### **8.2.2. Analysis methods**

The primary endpoint is the time to colorectal cancer screening. The date of the pre-intervention survey will be considered Day 0. The date of screening will be considered the date of the event. The date of follow-up phone call will be considered the date of event for subjects for whom a screening result is not recorded in the medical record and who self-report that screening was done. We will conduct a Cox proportional hazards regression model with study arm to evaluate our primary endpoint. In the per-protocol population, we will conduct similar analyses and include age group and gender as independent variables.

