## 8.3. Secondary endpoints

### 8.3.1. Definitions

#### 1) Colorectal cancer screening rates at 12 months

The secondary endpoint is whether a subject has had colorectal cancer screening at 12 months. Each subject will have an indicator of “Yes” or “No” for whether they were screened for colorectal cancer at 12 months. This will be determined by a review of subjects’ electronic medical records at 12 months post-randomization. Patient self-report on screening will be used for subjects for whom a screening result is not recorded in the EMR.

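### A subject with no EMR screening record who reports being screened is a non-event under section 8.2.1 and an event under sections 3.1 and 8.2.2

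*Combined protocol and SAP*

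**What the plan says.** Three current sections govern whether a subject has a primary event.

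- Section 8.2.1 (Definition) names one source: "This will be determined by a review of subjects' electronic medical records". It then adds: "Subjects for whom a screening result is not recorded in the EMRs will be deemed to have not had colorectal cancer screening".
- Section 3.1 defines the same endpoint by EMR review and self-report together, and says that subjects with no screening result in the "EMRs will be classified based on patient self-report of screening".
- Section 8.2.2 supplies an event date for those of them who say that they were screened: "The date of follow-up phone call will be considered the date of event for subjects for whom a screening result is not recorded".

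Two other places bear on the choice. Section 3 plans the contact that would collect the self-report: "Subjects who were not screened, per their electronic medical record, will be contacted via phone or mail to see if they were screened elsewhere". Section 8.3.1 defines the 12-month and 6-month secondary endpoints with the same sentence: "Patient self-report on screening will be used for subjects for whom a screening result is not recorded in the EMR".

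**The concern.** The conflict affects one group only: subjects with no EMR screening record who say that they were screened. Subjects with an EMR record are events under either rule, and subjects with neither a record nor a positive self-report are events under neither.

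For the affected group, the rule decides event status, event date and the number of events in the primary Cox analysis. Under section 8.2.1 the same person would be unscreened for the primary endpoint and a Yes for the 12-month secondary endpoint.

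Each rule also carries its own risk. EMR-only counting leaves real outside screenings as non-events, which can pull the hazard ratio towards 1. Self-report can differ by arm, because "This is an open-label study with no blinding". If the choice stays open until the data are in hand, there are in effect two primary analyses to pick from.

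**Working it through.** **1. Side by side.** Take a subject with no EMR record who reports an outside screening at a follow-up call.

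| Section | Status of this subject |
|---|---|
| 8.2.1, primary definition | not screened |
| 3.1, primary endpoint | screened |
| 8.2.2, primary Cox model | event, dated at the call |
| 8.3.1, 12-month secondary | Yes |

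No section ranks the two rules or confines either one to a sensitivity analysis. That alone establishes the point. The rest gives an idea of size.

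**2. The planned sample size.** Section 3.2 gives 50% and 65% screened by 6 months, a hazard ratio of 1.5 and 225 subjects. It states no power. Assume 80% power, two-sided alpha of 0.05, 1:1 allocation, exponential times and 12 months of follow-up for everyone.

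- HR = ln(0.35)/ln(0.50) = 1.515.
- Events (Schoenfeld) = 4 × (1.960 + 0.842)² / (ln 1.515)², which rounds up to 183.
- 12-month event probability: control 1 − 0.50² = 0.75; CRCRAT 1 − 0.35² = 0.8775; mean 0.81375.
- N = 183 / 0.81375 = 224.9, so 225.

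The planned figure is reproduced. It does not settle which rule was intended, because section 3.2 does not say whether its rates include self-reported screening.

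**3. Events at stake.** Expected events are 225 × 0.81375 = 183.1. If a share s is known only by self-report, equal in both arms, EMR-only counting removes 183.1 × s: about 18 events at 10%, 37 at 20% and 55 at 30%. The shares are assumptions; the documents give none.

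**4. Effect on the primary test.** Simulation with hazards ln 2/6 and −ln(0.35)/6 per month (rates taken as all-source), N = 225, censoring at 12 months, Cox Wald test at two-sided 0.05 and 6,000 replicates per cell (Monte Carlo error about 0.6 points). HR is the exponential of the mean log HR. The plan names no method for ties, so two are shown. With true screening dates the HR is 1.52 and power 79.5%.

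| Rule | s = 10% | s = 20% | s = 30% |
|---|---|---|---|
| EMR-only: HR | 1.42 | 1.37 | 1.31 |
| EMR-only: power | 61% | 47% | 34% |
| Self-report, calls at 6 or 12 months: power (Efron) | 79% | 78% | 77% |
| Same, Breslow | 78% | 75% | 73% |
| Self-report, all calls at 12 months: power (Efron) | 74% | 71% | 67% |
| Same, Breslow | 73% | 64% | 54% |

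As a cross-check, the Schoenfeld formula with the HR held at 1.5 and only the event count reduced gives 74%, 69% and 63% for EMR-only, against 78% with all 183 events. That is optimistic, because it leaves out the attenuation. With the HR taken instead from the reduced 12-month cumulative rates (1.39, 1.32, 1.28), it gives 56%, 39% and 29%. The simulated values lie between the two.

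**5. The risk on the other side.** With no true effect (both hazards ln 2/6), a 20% self-report-only share and calls at 6 or 12 months, suppose that 10%, 20% or 30% of unscreened CRCRAT subjects, and no controls, wrongly report screening at 12 months. The HR becomes 1.04, 1.08 or 1.12, and the two-sided rejection rate 5.8%, 7.4% or 11.8%. With no false reports it is 5.0%.

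**The case against.** The strongest reply is that the intended rule can be inferred. Section 8.2.2 dates events for exactly the disputed group, a sentence with no function if section 8.2.1 governs, and sections 3, 3.1 and 8.3.1 point the same way. Section 8.2.1 looks like a leftover. This makes the two readings unequally likely, and it supports the direction of the fix. It does not remove the conflict: the outlier is an explicit, unqualified rule in the formal definition of the primary endpoint.

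The power figures can also be challenged, and rightly. The self-report-only share is not in the documents. At smaller shares the same model gives EMR-only power of about 76% (2%) and 71% (5%). If the 50% and 65% rates are EMR-recorded, EMR-only counting keeps about 80%. Placing every call at 12 months fits poorly with the planned 6-month review, and false reports in one arm only are an extreme case. The size therefore runs from no loss to a large one.

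Two further points stand as limits on the remedy. An EMR-only sensitivity analysis cannot by itself separate reporting bias from missed outside screenings, since both would give a weaker result than the primary. And a call prompted by the 12-month review may fall after month 12; section 8.2.2 does not say whether it then counts. That gap exists already. At a 20% share, censoring such calls at month 12 gives about 74% power, against about 79% in the same run with calls at 6 or 12 months.

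Finally, the open-label design is a reason to prefer EMR-only. The text requires one stated rule; the choice belongs to the sponsor.

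**Conclusion.** The concern holds. The primary endpoint is not uniquely defined, so the primary result cannot be uniquely reproduced from the plan. This rests on the wording alone and must be resolved before analysis.

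The size is conditional. With all-source planned rates, exponential times and a self-report-only share of 10% to 30% that is equal in both arms, EMR-only counting gives 61% down to 34% power. Counting self-report does not fully restore the 80% available with true dates, because call dates replace screening dates. The benefit of counting self-report shrinks as the share falls and disappears if the planned rates were EMR-recorded.

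**What to change.** Replace the last two sentences of section 8.2.1 with the section 3.1 rule: screening is determined by EMR review and, where the EMR shows none, by the subject's own report, dated as in section 8.2.2. This agrees with sections 3, 3.1, 8.2.2 and 8.3.1. Name the EMR-only count, with self-reported screenings as non-events, as a sensitivity analysis, and acknowledge that a weaker result there has two possible explanations. If the sponsor prefers EMR-only as primary, sections 3.1 and 8.2.2 must change instead, and the two rules swap roles.

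Three clarifications could be made in the same edit:

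- how subjects with neither an EMR record nor a self-report are handled, consistent with section 8.1.2;
- which date applies to a self-report received by mail, since section 3 allows phone or mail and section 8.2.2 dates only a call;
- whether a self-report obtained after month 12 counts.

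The cost is SAP wording and one extra model run. No new data collection is needed, because section 3 already plans the contact. Its and/or wording and the limit of three contacts mean that self-report may not be obtained from everyone. The remaining downside is possible differential reporting in an open-label trial, which the sensitivity analysis exposes but cannot fully resolve.
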